Study Protocol

FREEZing-of-Gait Etiology–Phenotype–Outcome Pathway Cohort (FREEZE-Path Cohort)

NCT number: Not yet assigned

Protocol Version: V1.0

Date: October 20, 2025

1. Study Title

FREEZing-of-Gait Etiology–Phenotype–Outcome Pathway Cohort (FREEZE-Path Cohort)

2. Study Design

This study is a prospective, observational, multicenter cohort study designed to investigate the etiology, phenotypic heterogeneity, and longitudinal outcomes of freezing of gait (FOG) across different neurological conditions.

Participants will be followed for 36 months with repeated standardized clinical, gait, and functional assessments. The study does not assign any intervention and does not influence routine clinical management.

3. Study Objectives

3.1 Primary Objective

To establish a multicenter, cross-etiology FOG cohort and to characterize longitudinal changes in FOG burden across different underlying diseases.

3.2 Secondary Objectives

To identify etiological and phenotypic differences in FOG progression and outcomes.

To determine risk factors and predictors for incident FOG in patients at high risk.

To describe associations between real-world treatment exposures (pharmacological, neuromodulation, rehabilitation) and changes in FOG burden.

To develop and validate multimodal prediction and risk-stratification models based on clinical, gait, video, neuroimaging, electrophysiological, and speech features.

4. Study Population

4.1 Study Groups

FOG Group (n ≈ 500):

Patients with established freezing of gait.

High-Risk Group (n ≈ 200):

Patients with Parkinson's disease (PD) presenting gait or balance impairment but without FOG at baseline.

Total planned enrollment: 700 participants

Study centers: 1 coordinating center and 4 participating centers

4.2 Inclusion Criteria

- 1) Age 30–85 years
- 2) Presence of freezing of gait or non-freezing gait or balance impairment
- 3) Diagnosis of Parkinson's disease or related parkinsonian disorders according to established international criteria (including PD, PSP, MSA, DLB, CBD, vascular parkinsonism, or idiopathic normal pressure hydrocephalus)
- 4) Ability to complete gait and balance assessment tasks independently or with assistance
- 5) Ability and willingness to provide written informed consent

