6.1 Follow-Up Schedule

Participants will be assessed at:

Baseline

3, 6, 12, 18, 24, 30, and 36 months

Triggered visits will occur within one week after major events (e.g., first FOG episode, fall, surgery).

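### Section 4.2 as written admits FOG-free patients with non-PD diagnoses, but section 4.1 has no group for them

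*Protocol*

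**What the plan says.** Protocol section 4.1 sets up two groups. The FOG group (about 500) takes patients with established FOG and names no diagnosis. The high-risk group (about 200) takes patients with Parkinson's disease "presenting gait or balance impairment but without FOG at baseline". The same section gives "Total planned enrollment: 700 participants" and "Study centers: 1 coordinating center and 4 participating centers".

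Section 4.2 then gives one list of inclusion criteria for the whole study. Criterion 2 is "Presence of freezing of gait or non-freezing gait or balance impairment". Criterion 3 asks for Parkinson's disease or a related parkinsonian disorder, "including PD, PSP, MSA, DLB, CBD, vascular parkinsonism, or idiopathic normal pressure hydrocephalus". Neither criterion refers to the other or to the groups in section 4.1. The six exclusions in section 4.3 cover cognition, psychiatric disease, other medical conditions, recent major events, compliance with follow-up, and refusal of video or speech recording. None concerns diagnosis or FOG status. Section 5 specifies consecutive recruitment.

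**The concern.** The eligibility list and the group definitions describe different populations. The list lets in a FOG-free patient with any of the named diagnoses; the groups take a FOG-free patient only if the diagnosis is PD. If section 4.2 is applied as written, three things follow.

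- **Enrolment.** A FOG-free patient with a non-PD diagnosis takes a place in a total that is already fully allotted to two groups, and belongs to neither.
- **Incident FOG.** A first FOG episode in such a patient would trigger a visit under section 6.1. It would not count in the time-to-first-FOG outcome, which section 7.2 confines to the high-risk group.
- **Etiology comparison.** Section 8.2 compares FOG-burden trajectories across etiological subgroups and does not keep these patients out. If some centers admit them under section 4.2 and others refuse them under section 4.1, the FOG-free share within the non-PD etiologies would depend on the center. Part of any difference between etiologies could then reflect center practice.

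**Working it through.** **Planned total.** The group sizes in section 4.1 are approximate: 500 + 200 = 700. This reproduces the stated enrolment, so no third group is planned.

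**Who is admitted and who has a group.** Criterion 3 names 7 diagnoses: PD, PSP, MSA, DLB, CBD, vascular parkinsonism and iNPH. Criterion 2 allows 2 states: FOG, or no FOG with another gait or balance impairment. Applying sections 4.2 and 4.1 to each combination gives:

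| Diagnosis | State | Admitted by criteria 2 and 3? | Group in 4.1 |
|---|---|---|---|
| PD | FOG | Yes | FOG |
| PD | No FOG, impaired | Yes | High-risk |
| Each of the 6 others | FOG | Yes | FOG |
| Each of the 6 others | No FOG, impaired | Yes | None |

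- Admitted: 7 × 2 = 14 combinations.
- With a group: 7 (FOG, any diagnosis) + 1 (PD without FOG) = 8.
- Without a group: 14 − 8 = 6.

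The 6 does not depend on how the table is drawn. If FOG patients are also split by whether they have a further gait or balance impairment, there are 7 × 3 = 21 admitted combinations. Of these, 14 + 1 = 15 have a group, and 21 − 15 = 6 again have none. Criterion 3 introduces its list as examples, so 6 counts named diagnoses only.

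**Centers that must interpret the rule.** 1 + 4 = 5.

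**Does another passage settle the intent?** Section 3.1 aims "To establish a multicenter, cross-etiology FOG cohort", which favors reading the non-PD diagnoses as belonging to the FOG group only. Section 3.2 aims "To determine risk factors and predictors for incident FOG in patients at high risk" and does not name PD there. The first leans towards restriction and the second leaves the matter open. Neither is an eligibility rule.

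**The case against.** The best reply is that sections 4.1 and 4.2 both stand under Study Population and should be read together. On that reading, the groups are defined first and fill the 700, and section 4.2 lists criteria common to both. A participant must meet the list and also fit a group, so a FOG-free PSP patient has no place. The high-risk wording in section 3.2 is then simply the term that section 4.1 defines as PD, and section 7.2 uses it in the same way. The defect would be a missing cross-reference, and every consequence would be conditional. The protocol does not describe how centers screen, it does not say which groups enter the section 8.2 model, and a visit triggered by a first FOG episode does no harm in itself.

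Much of this stands. The restrictive reading is the likelier intent, and the evidence for the opposite intent is thin. Variation between centers is a possibility, not something the document shows. The effect on section 8.2 arises only if these patients enter that comparison, which a SAP may settle. The count of 6 says nothing about frequency.

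It does not remove the problem. No sentence makes fitting a group a condition of entry. A center that recruits consecutively and screens against sections 4.2 and 4.3 would enrol these patients and be following the protocol. An analysis rule written later cannot undo that.

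**Conclusion.** The concern holds. Sections 4.1 and 4.2 disagree on whether a patient with a non-PD diagnosis and no FOG may enter, and the eligibility list, as written, says yes. The extent is 6 of 14 combinations of named diagnosis and FOG status. The number of patients cannot be derived, because the protocol gives no case mix by diagnosis, and none is assumed here.

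Confidence is high for the wording, which needs only the text and a count. The effect on the etiology comparison rests on two assumptions: that centers resolve the conflict differently, and that the ungrouped patients are analysed under section 8.2. The point should be fixed before enrolment; it does not invalidate the study.

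**What to change.** Reconcile sections 4.1 and 4.2 before the first participant is enrolled. The sponsor must first say which population is meant.

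- **If FOG-free non-PD patients are not wanted:** make the FOG-free route in criterion 2 specific to Parkinson's disease, or add to section 4.2 that a participant must also fit one of the two groups in section 4.1. This is a one-line change.
- **If they are wanted:** define a group for them in section 4.1, divide the 700 again among the groups, and state in section 7.2 whether they enter the time-to-first-FOG outcome. This takes short edits to two sections and a new split of the total.

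Neither route adds patients, visits or procedures. The document is at V1.0, so the change is cheap now. Patients already enrolled under differing readings could not be un-enrolled later.

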4.3 Exclusion Criteria

- 1) Severe dementia (Mini-Mental State Examination score < 10)
- 2) Severe psychiatric disorders interfering with study participation
- 3) Severe cardiopulmonary, musculoskeletal, or other medical conditions significantly affecting gait safety
- 4) Stroke, fracture, or other major medical events within the past 3 months
- 5) Inability to comply with follow-up procedures
- 6) Refusal of video or speech data collection

5. Recruitment and Sampling

Participants will be recruited consecutively from neurology, neurosurgery, and rehabilitation clinics at participating centers. A consecutive sampling strategy will be used to minimize selection bias.

6. Study Procedures and Data Collection

6.1 Follow-Up Schedule

Participants will be assessed at:

Baseline

3, 6, 12, 18, 24, 30, and 36 months

Triggered visits will occur within one week after major events (e.g., first FOG episode, fall, surgery).

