6.2 Core Data Collection (All Centers)

Demographics and disease history

Motor and non-motor symptoms

Medication and treatment exposure

Standardized clinical scales:

New Freezing of Gait Questionnaire (NFOG-Q)

MDS-UPDRS II & III

MMSE, MoCA

PDQ-39

Berg Balance Scale, Mini-BESTest

Standardized gait-provoking tasks with synchronized video recording

Speech tasks using a fixed protocol

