7.1 Primary Outcome

Longitudinal change in FOG burden, measured by annualized change in NFOG-Q

total score over 36 months.

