8.1 General Principles

All analyses will be conducted using two-sided tests with a significance level of 0.05.

Statistical analyses will be performed using R or SPSS.

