8.2 Primary Analysis

Linear mixed-effects models will be used to evaluate longitudinal changes in FOG burden and to compare trajectories across etiological subgroups.

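### Do visits triggered by falls, first FOG or surgery bias the primary mixed-model comparison of NFOG-Q trajectories across etiologies?

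*Protocol*

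**What the plan says.** Protocol section 6.1 sets assessments at baseline and at "3, 6, 12, 18, 24, 30, and 36 months". It then adds, as a separate statement, "Triggered visits will occur within one week after major events (e.g., first FOG episode, fall, surgery". It does not say what is measured at a triggered visit.

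Section 6.2 lists NFOG-Q among the core scales at all centers, with no visit-by-visit table. Section 7.1 defines the primary outcome as "Longitudinal change in FOG burden, measured by annualized change in NFOG-Q" total score over 36 months. Section 8.2 reads "Linear mixed-effects models will be used to evaluate longitudinal changes in FOG burden and to compare trajectories across etiological subgroups". It gives no rule on which visits contribute.

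The protocol gives no rate of falls, surgery or first FOG for any etiology, and no assumed SD or effect size for NFOG-Q.

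**The concern.** A mixed model treats visit times as uninformative given the data already observed and the model. Fixed visits meet that condition. A visit prompted by a fall or a first freezing episode may not, because it may catch the patient on a bad day. Baseline has no triggered visit, so any excess falls on later times and tilts the slope upward. If one etiology falls more often, its curve would be tilted more, and the etiology comparison would partly reflect how often patients were sampled after events.

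The volume could be large. With about 500 FOG participants and an assumed 1 to 4 falls per year, triggered visits could rival the scheduled ones in number. At stake is the primary comparison, tested two-sided at 0.05 (section 8.1).

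**Working it through.** The protocol contains no figure to reproduce. All rates, SDs and excesses below are assumptions.

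**Visit counts (FOG group, n about 500, section 4.1)**
- Scheduled after baseline: 500 × 7 = 3,500.
- Triggered at 1 fall per year: 500 × 3 × 1 = 1,500. At 4 per year: 500 × 3 × 4 = 6,000. This supposes that every fall leads to its own completed visit. First FOG cannot be a trigger in this group, which already has FOG.

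**Conditions needed for bias in the etiology contrast**
1. NFOG-Q is taken at triggered visits and analysed. Sections 6.1, 6.2 and 8.2 do not say so.
2. The score at such a visit departs temporarily from the patient's own trajectory. This is plausible, but the protocol does not address it.
3. Trigger rates, or the size of the departure, differ by etiology. No rates are given. The one link in the text is that first FOG can arise only in FOG-free participants, a group that section 4.1 defines as having PD.

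**Simulation A.** 500 patients, two etiologies with the same true slope of 1.5 points/yr, the eight visits of section 6.1 plus triggered visits, and a mixed model with time, etiology, their interaction, and random intercept and slope. Baseline mean 15 (SD 5), slope SD 1, residual SD 3; 60 replicates per row. State dependence means that the trigger rate is multiplied by e^0.5 = 1.65 per 5 points of true current FOG level. The contrast is the slope in the low-rate etiology minus the slope in the high-rate one (truth 0).

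| Trigger rates/yr | State-dependent | Excess (points) | Slope, high-rate etiology: all visits / scheduled only | Contrast: all visits / scheduled only | SE of contrast |
|---|---|---|---|---|---|
| 1.0 vs 0.3 | no | 0 | 1.512 / 1.513 | −0.012 / −0.014 | 0.125 |
| 1.0 vs 0.3 | yes | 0 | 1.512 / 1.504 | −0.007 / −0.003 | 0.123 |
| 1.0 vs 0.3 | no | 2 | 1.577 / 1.517 | −0.048 / −0.008 | 0.125 |
| 1.0 vs 0.3 | yes | 2 | 1.611 / 1.499 | −0.082 / −0.016 | 0.127 |
| 2.0 vs 0.5 | yes | 2 | 1.641 / 1.503 | −0.051 / 0.012 | 0.124 |
| 1.0 vs 1.0 | yes | 2 | 1.610 / 1.510 | −0.016 / −0.016 | 0.124 |
| 1.0 vs 0.3 | yes | 4 | 1.700 / 1.500 | −0.122 / −0.012 | 0.131 |

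The Monte Carlo error of the all-visits contrast is 0.013 to 0.020.

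- Rows 1 and 2: unequal rates, without and with dependence on the modelled trajectory, give no detectable bias.
- Row 6: equal rates with a 2-point excess raise the slope by 1.610 − 1.510 = 0.100 and leave the contrast where the scheduled visits put it.
- Rows 3 to 5: the contrast shifts, net of the scheduled-only fit, by 0.048 − 0.008 = 0.040, 0.082 − 0.016 = 0.066 and 0.051 + 0.012 = 0.063. These are 0.32, 0.52 and 0.51 SE. By normal approximation a shift of that size takes a 5% two-sided test to about 6% to 8%.
- Row 7: 0.122/0.131 = 0.93 SE, or (0.122 − 0.012)/0.131 = 0.84 SE net. The approximation gives about 13% to 15%.

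Sixty replicates are too few to estimate rejection rates directly.

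**Simulation B.** True slope 1 point/yr in both etiologies, intercept SD 4, slope SD 1, error SD 1.5, and a fluctuating process of SD 3 that drives both score and fall risk (risk 1.6 to 1.8 times higher per SD of worsening). Fall rates ranged from 0.25 to 6 per year; 120 per group, 45 replicates. Including triggered visits added a false slope difference of 0.02 to 0.09 points/yr (2% to 9% of the slope) and raised the 36-month level of the higher-falling etiology by 0.29 to 0.35 points.

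**The case for a change.** The best case for a change has four parts.

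- Whether sites complete NFOG-Q at a triggered visit is a data-collection instruction, which an analysis plan written later cannot give. That stands as an observation: the protocol is silent. But neither answer damages the primary analysis. If the scale is not completed there, no score can enter the model. If it is, the score is an extra record beside an unaltered set of scheduled ones and can be left out.
- The overall slope moves even when trigger rates are equal (0.100 points/yr, about 7%, in the sixth row). That stands too, but only if triggered scores are analysed and carry a 2-point excess.
- First FOG is by definition a PD-only trigger in the high-risk group, and section 7.1 does not confine the primary outcome to the FOG group. This gives some textual support for unequal triggering. Falls and surgery can occur in any group, however, and no rates are given.
- A test size of 13% to 15% would matter. It comes from the 4-point excess, the most extreme input tried; the 2-point rows with unequal rates give about 6% to 8%.

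A sentence restricting the model to scheduled visits would be cheap and harmless. Cheapness does not show that the present text leads to a wrong result.

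**Conclusion.** The concern identifies a real feature of the design but not an error in the plan. "Linear mixed-effects models will be used to evaluate longitudinal changes in FOG burden" names a model class. It neither admits nor excludes triggered scores, and the choice of analysis visits is commonly settled in the statistical analysis plan, which is not shown here. A sensible reading is available: annualized change over 36 months rests on the scheduled visits, and triggered visits serve to date events for the time-to-event and falls outcomes in sections 7.2 and 8.3. That purpose is an inference, since the protocol does not state it.

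If triggered scores were included after all, the false etiology difference would be about 0.02 to 0.12 points per year under the inputs tried, and below one standard error in the most extreme case. That size depends on assumed trigger rates, an assumed transient excess and assumed variances, and a larger excess or more uneven rates would increase it. With scheduled visits only, the contrast in simulation A stayed between −0.016 and 0.012, within Monte Carlo error of zero. This is a gap that analysts can be expected to fill sensibly, and no change is called for.

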6.2 Core Data Collection (All Centers)

Demographics and disease history

Motor and non-motor symptoms

Medication and treatment exposure

Standardized clinical scales:

New Freezing of Gait Questionnaire (NFOG-Q)

MDS-UPDRS II & III

MMSE, MoCA

PDQ-39

Berg Balance Scale, Mini-BESTest

Standardized gait-provoking tasks with synchronized video recording

Speech tasks using a fixed protocol

6.3 Extended Data Collection (Optional Centers)

Instrumented gait analysis parameters

Quantitative balance measurements

Structural MRI (3.0T)

Functional MRI

EEG or fNIRS

PET imaging (if clinically available)

6.4 Biospecimens

No biospecimens will be collected, stored, or retained for this study. Only results from routine clinical laboratory tests, if already available, may be extracted from medical records.

7. Outcome Measures

7.1 Primary Outcome

Longitudinal change in FOG burden, measured by annualized change in NFOG-Q

total score over 36 months.

7.2 Secondary Outcomes

Time to first FOG occurrence (high-risk group).

Frequency of falls and fall-related injuries.

Changes in quality of life (PDQ-39).

Changes in gait parameters.

Changes in balance parameters.

Changes in functional brain network connectivity, assessed by resting-state functional MRI (fMRI)

8. Statistical Analysis

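### Must the resting-state fMRI outcome in section 7.2 be restricted because section 6.3 collects fMRI only at optional centers?

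*Protocol*

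**What the plan says.** Section 7.2 ends its list of six secondary outcomes with "Changes in functional brain network connectivity, assessed by resting-state functional MRI (fMRI"). The first entry in that list carries a population label, "Time to first FOG occurrence (high-risk group"); the fMRI entry carries none.

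Data collection is split into two tiers. Section 6.2, "Core Data Collection (All Centers"), covers demographics, scales, video-recorded gait tasks and speech, and includes no imaging. Section 6.3, "Extended Data Collection (Optional Centers"), is the only place where fMRI is collected, entered simply as "Functional MRI".

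Section 6.1 gives one schedule for participants in general, namely baseline and then "3, 6, 12, 18, 24, 30, and 36 months". It ties no procedure to any particular visit. Section 4.1 gives "Study centers: 1 coordinating center and 4 participating centers" and "Total planned enrollment: 700 participants", without saying which centers, or how many, will do the extended collection.

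**The concern.** A change outcome needs at least two comparable scans in the same person. The protocol commits no center to scanning and marks no visit as a scan visit, so paired scans are not visibly secured. An analysis plan written later can define a subset, but it cannot produce a baseline scan that was never acquired.

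The second worry is about scope. Section 7.2 restricts one outcome to a named group and leaves the fMRI outcome unrestricted, so a reader might take the fMRI result to speak for the whole cohort. The consecutive sampling in section 5 governs who is enrolled and not who is scanned, so it would not protect a result from a subset against selection. At stake would be a secondary imaging result drawn from fewer people than its wording suggests.

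**Working it through.** The protocol gives no fMRI sample size, effect size, SD or precision target, so there is no stated figure to reproduce. The check is a comparison of the text, followed by an illustration of size.

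**Text**

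1. *Sections 7.2 and 6.3.* The outcome line names no population. The collection section states in its heading that the tier is optional. Read together, they limit the outcome to people scanned at centers that take up the tier. Neither section says that everyone is scanned.
2. *The label on time to first FOG.* Section 4.1 defines the FOG group as already having freezing, so a first occurrence is possible only in the high-risk group. The label marks who can have the event. It says nothing about where data are available, so its absence from the fMRI line does not imply cohort-wide coverage.
3. *Resting-state and the section 6.3 entry.* Section 6.3 names the modality and section 7.2 the type of acquisition used for the outcome. They are compatible.
4. *Visits.* Section 6.1 assigns no procedure to any visit, and this is as true of NFOG-Q and PDQ-39 as of fMRI. The natural reading is that both tiers are collected within that schedule. An outcome defined as a change already implies repeat scans, although their number is not given.
5. *Section 8.* It specifies mixed models for FOG burden and Cox models for time-to-event outcomes. It contains no fMRI model, and so no cohort-wide fMRI inference.

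**Size (illustrative)**

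Inputs from section 4.1: 1 + 4 = 5 centers and 700 participants. Assumptions not in the protocol: equal enrolment, the number k of scanning centers, and 50-80% of their participants having paired scans.

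- Per center: 700/5 = 140.
- Maximum coverage, 140k/700: 20% for k = 1, 40% for k = 2, 60% for k = 3.
- Interval width relative to all five centers at the same paired share, sqrt(5/k): 2.24, 1.58 and 1.29 for k = 1, 2 and 3.
- Paired n = 140 × k × (0.5 to 0.8); 95% half-width for a mean standardised change = 1.96/sqrt(n):

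| k | Paired n | Half-width (SD) |
|---|---|---|
| 1 | 70-112 | 0.23-0.19 |
| 2 | 140-224 | 0.17-0.13 |
| 5 | 350-560 | 0.10-0.08 |

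The sqrt(5/k) ratio would hold for any outcome measured at k of five equal centers, so it does not point to a fault in this plan. The text allows anything from 0 to 5 scanning centers.

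**The case for a change.** The strongest case for a change is that what is collected, where and when belongs to the protocol, and that a missed baseline scan is lost for good. Three points support it. Section 2 describes the repeated assessments as clinical, gait and functional and does not mention imaging. Section 4.3 excludes people who refuse video or speech recording but has no counterpart for MRI, so scanning is not a condition of entry even at a scanning center. And fMRI is the listed outcome that most plainly lacks a core data source, since balance scales and gait tasks are in section 6.2. The suggested edit would take only a few lines.

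Part of this stands. The protocol is silent on scanning centers and scan visits, and a later analysis plan could not recover scans that were not taken. But silence is not a wrong schedule, and nothing in the text shows that paired scans would go unacquired. Nor does it show that the scanned group would be self-selected: section 6.3 makes participation optional for centers and does not say on what basis they join. Binding those centers to a common scan schedule would narrow a tier that was deliberately left optional. That is an operational choice for the sponsor and does not correct an error. Moving the outcome to exploratory status would need a class of outcome that section 7 does not have.

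**Conclusion.** The observation is accurate, but no change follows. Sections 6.3 and 7.2 are consistent, the optional tier is disclosed, and no cohort-wide fMRI conclusion is planned. The details left unwritten (which centers, which scan visits, a subset label) are ones that the sponsor and analysts would ordinarily settle by analysing participants with repeat resting-state scans and reporting the result for that group.

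The consequence is confined to the last of six secondary outcomes in an observational cohort. The primary outcome, annualized NFOG-Q change, uses a measure in the all-center core set and is untouched. The coverage and precision figures illustrate scale only. Even the one-center case leaves a usable subset estimate if the assumed paired share holds. If no center took up fMRI, this one outcome would go unreported and the rest of the study would be unaffected.

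The conclusion rests on reading the section 6.1 schedule as applying to both collection tiers, and on the fMRI result being reported for those scanned. A report that presented it as a finding for all 700 participants would be open to criticism, but the protocol does not propose that.
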